7.3. Estimation of Incomplete Data

Due to this relatively small scale of clinical trial, any incomplete observation will be considered as missing data with no specific estimation for the incomplete data.

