5.3. Withdrawal Criteria

Patients with any of the following conditions may be withdrawn from the trial:

5.3.1. Patients decide to withdraw their consent at any time-point.

5.3.2. Patients indicate the status of lack of efficacy which is of clinical significance judged by the investigators that may lead to permanent damage to the patients.

5.3.3. Investigators consider that there is of safety concerns for the patients to remain in the trial (such as development severe medical disease).

5.3.4. Lost of follow-up or death.

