7. STATISTICAL ANALYSIS

7.1. Evaluability

Patients receiving baseline screening and treatment will be considered as intent-to-treat (ITT) population. The ITT population with the following conditions will be considered as per-protocol (PP) population:

- 1. Not taking any prohibited medications
- 2. Fulfilling all entry criteria
- 3. Have treatment visit and post-treatment evaluations on the primary endpoint

The efficacy evaluation will be performed on both the ITT and PP datasets while the safety evaluations will be performed only on the ITT datasets. The primary conclusions will be made for the primary and secondary endpoints on the ITT patients.

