7.2 Analysis

The statistical objective of this study is to demonstrate that the efficacy of ESWT is superior to placebo with respect to the decreases of UAB symptom score, and PVR. The safety profile of ESWT or placebo for the either group of treatment of patients with DU/UAB will also be confirmed.

Primary Efficacy Endpoint

The efficacy of ESWT treatment will be evaluated for:

(1) Net changes of the mean post void residual (PVR) volume (mL) from baseline to 1 month after the treatment day.

Secondary Efficacy Endpoint

The efficacy of ESWT will be evaluated for:

- (1) Net change of the following parameters from baseline to 1 month after the treatment day: functional bladder capacity (FBC), voiding frequency at daytime and voiding frequency at night time, incontinence, as record in 3-day voiding diary.
- (2) Global response assessment (GRA) of satisfaction by the patient (categorized into -3, -2, -1, 0, 1, 2, 3, indicating markedly worse to markedly improved) at 1 month after the treatment day. An improvement of GRA by 2 scales at 1 month is considered effective.
- (3) Net changes of the maximum flow rate, voided volume, Pdet@Qmax, and postvoid residual volume from baseline to 1 month after the treatment day.
- (4) Changes of Underactive Bladder Questionnaire (UAB-Q) score.
- (5) Changes of urinary nerve growth factor and cytokines level from baseline to 1 month after treatment day.

Voiding frequency at daytime and nighttime is measured as mean of the three-day voiding diary preceding the scheduled visit and the record days are 3 days.

Net change of each efficacy item will be analyzed by paired t-test between baseline and post-treatment in the treatment group and controlled group. The net changes of each efficacy item will be analyzed by ANOVA test to compare between treatment group and controlled groups. The global response assessment by the patients will be analyzed by Fisher exact test between the treatment and controlled groups.

All efficacy variables will be reported of respective point estimated and 95% confidence interval. Comparison tests will be reported of respective p value.

Secondary Safety Endpoints

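### The primary result labelled ITT is an observed-case analysis: treated patients without a 1-month PVR drop out of it, the PP set omits the same patients, and no missing-data sensitivity analysis is planned

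*SAP*

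**What the plan says.** - **Population.** SAP 7.1: "Patients receiving baseline screening and treatment will be considered as intent-to-treat (ITT) population". No post-treatment value is required. The same section adds: "The primary conclusions will be made for the primary and secondary endpoints on the ITT patients".
- **Test.** SAP 7.2: "The net changes of each efficacy item will be analyzed by ANOVA test to compare between treatment group and controlled groups". The primary item is the change in PVR from baseline to 1 month.
- **Missing values.** SAP 7.3: "any incomplete observation will be considered as missing data with no specific estimation for the incomplete data". The reason given is "Due to this relatively small scale of clinical trial".
- **Second dataset.** The third PP condition in SAP 7.1 is "Have treatment visit and post-treatment evaluations on the primary endpoint".
- **Expected loss.** SAP 7.4 assumes 20% drop-out, with 60 enrolled and 48 evaluable. Protocol 4.1 gives enrolment as approximate.
- **Withdrawal.** Protocol 5.3: "Patients with any of the following conditions may be withdrawn from the trial". The list includes "lack of efficacy which is of clinical significance judged by the investigators that may lead to permanent damage to the patients", safety concerns and loss to follow-up.
- **Visits.** Protocol 5.1 counts the primary end-point evaluation among the visits the study requires. Protocol 5.2.8 times that visit (V7) from V6. Protocol section 2 and SAP 7.2 place the endpoint one month after the treatment day.

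**The concern.** A change score cannot be formed without a 1-month PVR, and SAP 7.3 rules out estimating one. SAP 7.1, 7.2 and 7.3 together therefore make the primary result an observed-case comparison, although SAP 7.1 calls it ITT. SAP 7.3 discloses that nothing is estimated, but no section says that treated patients are left out of the primary test.

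The usual second look does not help. The PP set excludes the same patients and may exclude others as well, so agreement between ITT and PP says nothing about the missing ones.

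The observed-case difference is trustworthy if loss is unrelated to outcome. Withdrawal for lack of efficacy, or for safety (urinary retention is a listed local adverse event), may break that condition. A reader of the planned outputs could not judge how strongly a positive or negative finding depends on it.

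**Working it through.** **Inputs from the documents.** Difference 50 mL, SD 60 mL, 24 per arm evaluable, two-sided alpha 0.05, 20% drop-out, 60 enrolled (SAP 7.4); 1:1 allocation (Protocol section 3), so 30 per arm. Everything said below about who drops out is assumed.

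**1. The plan's own figures.** SE = 60 × √(2/24) = 17.32 mL. The noncentral t with 46 df gives power 0.807, matching the stated 80.677%. Enrolment is 48/(1 − 0.20) = 60, also matching. The smallest significant observed difference is 2.013 × 17.32 = 34.9 mL. If 12 losses fall unevenly, from 6/6 to 12/0, power moves only from 80.7% to 78.1%. The count of losses is therefore not the issue; who is lost may be.

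**2. Same mechanism, same rate, no true effect.** The bias is 0.

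**3. One common outcome-dependent rule, true effect 50 mL.**

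| Assumed rule | Lost, ESWT / placebo | Observed difference |
|---|---|---|
| Logistic in standardised improvement, slope 1, 20% overall | 14.3% / 25.7% | 44.5 mL |
| Same, slope 2 | 11.6% / 28.4% | 38.4 mL |
| Random 25% loss unless improvement exceeds the placebo mean by 75 mL (1.25 SD) | 16.5% / 22.4% | 53.0 mL |

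Power under the two logistic rules is about 76% and 69%. The third rule moves the estimate the other way, so the form of the rule decides the direction.

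**4. Unequal loss, no true effect, poorer responders more likely to leave (logistic, slopes 1 and 2).** Loss of 30% in one arm and 10% in the other gives 9.7 or 13.9 mL in favour of the arm with more loss. A 25%/15% split gives 4.8 or 6.9 mL.

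**5. Tipping point, 24 observed and 6 lost per arm.** If the lost ESWT patients did worse than the observed ones by δ, and lost placebo patients resembled observed ones, the all-treated difference is d − (6/30)δ. With the SE held at 17.32, significance is lost at δ = (d − 34.9)/0.2. The range also covers proper normal imputation with Rubin variance.

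| Observed d | p, observed cases | δ at which significance is lost (Rubin / fixed SE) |
|---|---|---|
| 40 mL | 0.025 | 21.7 / 25.7 mL |
| 45 mL | 0.013 | 44.4 / 50.7 mL |
| 50 mL | 0.006 | 65.9 / 75.7 mL |

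The reverse also occurs. An observed 30 mL (p=0.090) becomes significant if only the placebo losses did worse, by 24.3 (fixed SE) to 28.8 mL (Rubin). An equal 50 mL shift in both arms leaves the difference unchanged (Rubin p 0.035 at 40 mL, 0.009 at 50 mL).

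**6. No improvement in k of the 6 lost ESWT patients (fixed SE).** This also assumes a placebo mean change of about zero. At d = 40, k = 3 gives 40 − 40 × 3/30 = 36.0 mL (p=0.043), and k = 4 gives 34.7 mL (p=0.051). At d = 50, all 6 give 40 mL (p=0.025).

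**The case against.** The strongest defence is that the rule is disclosed, a reason is given, and the sample size openly counts 48 of 60. All true. Small size is also a fair argument against making a complex imputation the primary analysis. But inflating enrolment protects power when loss is random; it does not address loss related to outcome. Nor does small size argue against one simple check, since a few patients can decide a borderline result.

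A second defence is that the lack-of-efficacy rule is narrow and discretionary, so most loss may be unrelated to outcome. This has force. If only a quarter of the 20% loss follows the logistic rules and the rest is random, a true 50 mL appears as 48.1 or 45.4 mL, with power about 79% or 77%. By the figures above, a result at the design effect is also hard to overturn.

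A third is that a tipping point cannot identify why patients left. That is correct. It shows only how large a departure would change the conclusion.

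A reader might go further than the documents allow in four ways:

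- **That the withdrawal rule biases only against ESWT and costs only power.** The 53 mL example shows that this depends on the assumed form.
- **That the plan favours ESWT.** Under no effect this needs loss that differs between arms, which no passage documents.
- **That at most 12 values can be missing.** The 20% is a planning allowance, and enrolment is approximate.
- **That patients who stop early have no visit or date for the primary measurement.** Protocol 5.1 already requires the visit. The timing anchor is ambiguous, not absent.

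**Conclusion.** The point holds. The primary result is observed-case among ITT patients, the PP set cannot test the loss, and no other missing-data analysis is stated. This follows from SAP 7.1, 7.2 and 7.3 without any assumption.

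Whether the result would be biased, by how much, and in which direction cannot be known from the documents. The illustrations rest on SD 60 mL, 30 per arm, about 20% loss and assumed drop-out rules. Under them the effect runs from none to about 14 mL, in either direction. In practice a borderline result, roughly 35 to 45 mL, would be open to doubt, while one near the 50 mL design effect would be fairly robust.

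The primary test remains usable and the sample-size figures are correct. This should be changed, but it does not invalidate the design.

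**What to change.** 1. **Label and report.** Keep the primary ANOVA. Describe it as observed cases among ITT patients, and report by arm the number of missing 1-month PVR values and the reasons.
2. **One sensitivity analysis on all treated patients.** Prespecify a delta-adjusted tipping point: multiple imputation within arm from baseline PVR, Rubin variance, and the shift varied separately in each arm over a stated range and reported in mL. Separate shifts matter because the effect can go either way.
3. **Collection and timing.** State that the end-point visit required by Protocol 5.1 also applies to patients who stop sessions but keep consent, and that their PVR enters the ITT analysis. Reconcile the timing anchor: Protocol 5.2.8 runs from V6, while Protocol section 2 and SAP 7.2 refer to one month after the treatment day.

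The cost is a few sentences in the SAP and protocol and a modest extra analysis. The primary test and sample size do not change. The downside for the sponsor is that a borderline result may look less robust.

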7.4 Sample Size

We used PASS 14 to calculate power for this study. Group sample sizes of 24 and 24 achieve 80.677% power to reject the null hypothesis of equal means when the population mean difference (Net changes of the mean post void residual (PVR) volume (mL) from baseline to 1 month after the treatment day) is -50.0 with a standard deviation for both groups of 60.0 and with a significance level (alpha) of 0.050 using a two-sided two-sample equal-variance t-test. According to 20% of the patient's drop-out rate, the number of subjects is set to 60, and the evaluator is 48 to get enough verification power.
